8.6.1.3 The ASES score

The ASES score is developed by the Society of the American Shoulder and Elbow Surgeons for the assessment of shoulder function ([Richards et al 1994](#)). The ASES score is self-administered and has 17 questions in the areas of symptoms and functions. The severity of pain is graded on a 10 cm visual analog scale that ranges from 0 (no pain at all) to 10 (pain as bad as it can be). The recall period is the current point in time. The tool is filled in by the patient at visits specified in the [Assessment schedule](#).

Details of the ASES are outlined in the SOM.

8.6.1.4 EuroQuol 5D (EQ-5D-5L)

The EQ-5D-5L is a widely used, self-administered questionnaire designed to assess health status in adults. The purpose of the EQ-5D-5L in this study is to assess the general health status of the patients. The measure is divided into two distinct sections. The first section includes one item addressing each of five dimensions (mobility, self-care, usual activity, pain/discomfort, and anxiety/depression). Subjects rate each of these items from : "no problem", "slight problems", "moderate problems", "severe problems", "extreme problems/unable" A composite health index is then defined by combining the levels for each dimension. The second section of the questionnaire measures self-rated (global) health status utilizing a vertically oriented VAS where 100 represents the "best possible health state" and 0 represents the "worst possible health state." Respondents are asked to rate their current health by placing a mark along this continuum. The recall period is "today," and the questionnaire requires approximately 5 to 10 minutes to complete.

The EQ-5D-5L contains six items designed to assess health status in terms of a single index value or health utility score. One of the strengths of the EQ-5D-5L approach is that it allows "weighting" by the subject of particular health states and the generation of subject utilities. Published weights are available that allow for the creation of a single summary health utility score. Overall scores range from 0 to 1, with lower scores representing a higher level of dysfunction. The EQ5D is filled in by the patient at Day 1 prior to drug administration and at visits specified in the [Assessment schedule](#).

Details of the EQ5D are outlined in the SOM.

8.6.1.5 Patient's assessment of tendinopathy pain intensity and change in pain medication

The patient will assess his/her pain in a PRO diary once per day rating the pain during the previous 24 hours. The patient's assessment of pain will be performed using 100 mm visual analog scale (VAS) ranging from "no pain" to "worst possible pain" after the question "*Please rate the severity of your pain at its worst during the last 24 hours by marking an X on the line below*".

Similarly, the patient should note down whenever he/she has changed the NSAID/acetaminophen intake.

8.6.1.6 Patient's global assessment of disease activity

The patient's global assessment of disease activity will be performed using 100 mm VAS ranging from "no activity" to "most active", after the question "*Please indicate with a vertical mark (|) through the horizontal line the global activity of your disease in the last 24 hours*".

The patient's global assessment of disease activity is filled in by the patient at Day 1 prior to drug administration and at visits specified in the [Assessment schedule](#).

8.6.2 Clinician reported outcome (CRO) efficacy measures collected in the trial for secondary objectives

Physician's global assessment of disease activity

The physician's global assessment of disease activity will be performed using 100 mm VAS ranging from no disease activity to maximal disease activity, after the question "*Considering all the ways the tendinopathy affects your patient, please indicate with a vertical mark (|) through the horizontal line how well his or her condition is today*". To enhance objectivity, the physician must not be aware of the specific patient's global assessment of disease activity, when performing his own assessment on that subject.

The physician's global assessment of disease activity is filled in by the investigator at Day 1 prior to drug administration and at visits specified in the [Assessment schedule](#).

8.6.3 Imaging efficacy measures collected in the trial for secondary and exploratory objectives are:

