8.6 Efficacy

8.6.1 The PRO efficacy measures, primary and secondary objectives:

The impact of tendinopathy on various aspects of patient's health-related quality of life (QoL) will be assessed by the following instruments:

- The WORC score
- The QuickDASH score (in case available in local language/dialect)
- The ASES score
- The EQ5D-5L score
- Patient's global assessment of disease activity (VAS)
- Patient's assessment of tendinopathy pain intensity (VAS)

Daily assessments of pain intensity, as well as any changes in concomitant pain medication will be recorded in the patient diary.

All questionnaires will be available, in the local languages of the participating countries. The patients will be asked to fill in these PROs at the clinic at the visits specified in the [Assessment schedule](#).

Subjects should be given sufficient instruction, space, time and privacy to complete all study PROs. The study coordinator should check the responses to the questionnaire for completeness and encourage the subject to complete any missing responses. If subjects experience any difficulties with submission after they complete the PROs, the study staff should assist them with submitting their PRO responses. Attempts should be made to collect responses to all PROs for all subjects, including patients who prematurely discontinue prior to the study evaluation completion visit. However, if subjects refuse to complete PROs, this should be documented in study source records. Subject's refusal to complete study PROs are not protocol deviations.

Guidelines for administering the PRO questionnaires can be found in SOM.

Completed questionnaires and patient diaries will be reviewed and examined by the investigator, before the clinical examination, for responses that may indicate potential AEs or SAEs. The investigator should review not only the responses to the questions in the questionnaires but also for any unsolicited comments written by the subject. If AEs or SAEs are confirmed, then the physician must record the events as per instructions given in [Section 9.1](#) and [Section 9.2](#) of the protocol. Investigators should not encourage the subjects to change the responses reported in the completed questionnaires.

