11.5 Analysis of secondary variable(s)

Secondary variables include:

- Change from baseline in WORC score at weeks 2, 4, 8, 12, 18 and 24
- Disability of Arm, Shoulder and Hand Questionnaire (QuickDASH) score at weeks 2, 4, 8, 12, 14, 18 and 24
- American Shoulder and Elbow Surgeons Shoulder Evaluation Form(ASES) score at weeks 2, 4, 8, 12, 14, 18 and 24
- EQ5D score at weeks 2, 4, 8, 12, 14, 18 and 24
- Pain score using a VAS scale (considering the last 24 hours) at weeks 2, 4, 8, 12, 14, 18 and 24
- Patient global assessment (PGA) score using a VAS scale (considering the last 24 hours), at weeks 2, 4, 8, 12, 14, 18 and 24
- Physician global assessment (PhGA) score using a VAS scale (considering the last 24 hours), at weeks 2, 4, 8, 12, 14, 18 and 24
- MRI Sein score at weeks 8, 14 and 24

Secondary variables (except Sein score) will be summarized descriptively and analyses similar to the primary analysis will be performed.

The secondary endpoint (Sein MRI score at week 14) will be analyzed by ordinal categorical regression. A model with an additive treatment effect on the cumulative logistic scale will be used, and the common treatment effect estimated and reported together with 90% asymptotic two-sided confidence intervals. Baseline SEIN score will be included as a covariate and the stratification factors, partial tear/no tear and previous steroid injection (yes/no) will be included in the model as fixed effects.

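### The protocol has the investigator read the patient's global score before examining the patient, yet requires that score to be unknown when the physician global is rated

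*Protocol*

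**What the plan says.** Protocol section 8.6.1 lists the instruments that the patient completes, and one of them is "Patient's global assessment of disease activity (VAS". On where they are completed it says: "The patients will be asked to fill in these PROs at the clinic at the visits specified in the" assessment schedule. It then adds a safety step: "Completed questionnaires and patient diaries will be reviewed and examined by the investigator, before the clinical examination, for responses that may indicate potential AEs". Serious events are included. The review extends to the answers themselves: "The investigator should review not only the responses to the questions in the questionnaires but also for any unsolicited comments written by the subject". No instrument is left out of it.

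Protocol section 8.6.2 describes the one clinician-reported efficacy measure in the visible text. To protect objectivity it requires that "the physician must not be aware of the specific patient's global assessment of disease activity, when performing his own assessment on that subject". It also names the rater: "The physician's global assessment of disease activity is filled in by the investigator at Day 1 prior to drug administration", and again at the scheduled visits.

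The endpoint is defined in protocol sections 2.2 and 11.5 as "Physician global assessment (PhGA) score using a VAS scale (considering the last 24 hours"), and SAP section 6.2.1 keeps the same recall period and calls it a score of disease activity. The item printed in section 8.6.2 instead asks the physician how well the patient's condition is on the day, to be marked on a line from no disease activity to maximal disease activity.

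**The concern.** Two instructions to the same role pull against each other. The safety step puts the patient's global mark in front of the investigator before the examination. The masking rule says that the same mark must be unknown when the investigator rates.

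The primary endpoint, the WORC, is reported by the patient, as are most secondary endpoints. The PhGA is the only visible clinician rating, and SAP section 6.2.4 analyses it in the same way as the primary. A reader of the results may take agreement between the physician and patient globals as separate clinical support. That support is weaker if the rater may have just seen the patient's mark.

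The item wording adds a smaller problem. The question is about wellness and the line is about activity, so a rater who answers the question literally could mark a patient who is doing well towards the wrong end. The recall period also differs from that of the endpoint and from that of the patient global item.

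**Working it through.** No figure in either document depends on this point, so there is nothing to recompute. The check sets the instructions side by side.

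1. **Same role.** The reviewer in section 8.6.1 is the investigator. The PhGA rater in section 8.6.2 is the investigator. Neither document assigns the tasks to two people.
2. **Same visits.** Protocol section 11.5 gives Weeks 2, 4, 8, 12, 14, 18 and 24 for both globals. Section 8.6 adds Day 1 before dosing for both. That makes 1 + 7 = 8 occasions per patient.
3. **Same content.** The patient global is one of the listed instruments, the review covers responses, and no exception is made. After the review, the rater has seen the mark.
4. **Order for a single rater.** Section 8.6.1 requires the review to precede the clinical examination. Section 8.6.2 requires the PhGA to be marked while the patient global is unknown, hence before the review. Together they give: PhGA, then review, then examination. The physician would be rating disease activity before examining the patient.
5. **Other ways out.** A second investigator could rate, or the patient global could be held back from the review. Neither document provides for either.
6. **Where an order could be set.** Protocol section 10.3 leaves details of diary, patient-reported and clinician-reported data collection to the site operations manual, which is not among the documents. An order there that put the PhGA after the examination but before the review would still depart from section 8.6.1.
7. **Item against endpoint.**

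| | Question | Anchors | Recall |
|---|---|---|---|
| PhGA endpoint (protocol 2.2, 11.5; SAP 6.2.1) | disease activity (named in SAP 6.2.1) | not stated there | last 24 hours |
| PhGA item (protocol 8.6.2) | how well the patient is | no to maximal disease activity | today |
| Patient global item (protocol 8.6.1.6) | activity of the disease | no activity to most active | last 24 hours |

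The PhGA item differs from its endpoint in recall and from its own anchors in direction.

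**The case against.** The best answer is that the plan is unspecific here and not contradictory. Section 8.6.1 orders the review only against the clinical examination, and nothing says that the PhGA belongs to that examination or follows it. Marking the PhGA first would comply with both rules, and the site operations manual may require that or something equivalent. Table 8-1, as far as it can be read, schedules the formal physical examination only at screening, baseline and end of study, so it is unclear what a clinical examination means at the visits between.

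Much of this stands. A reader might infer that every site breaks the masking rule at every efficacy visit. The documents do not show that, because a compliant order exists and may be prescribed elsewhere. What remains is that the compliant order for one rater places a clinical judgement before the examination, which is an unlikely intention. Investigators also undertake in section 12.2 to follow all protocol instructions, so sites left to resolve this may do so differently.

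A reader might also infer that the PhGA largely repeats the patient's score. No document gives a basis for that, and the amount of anchoring cannot be derived. The masking rule covers the patient global alone. The PhGA item asks the physician to weigh every way the condition affects the patient, which draws on what the patient says. Independence from the WORC, pain scale or diary was never promised.

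Finally, patients and raters are blinded to treatment (section 6.4), the SAP plans no analysis of agreement between the two globals, and the centrally read MRI score is a further measure that the patient does not report. These points stand and limit the consequence.

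**Conclusion.** The concern holds in a limited form. The protocol sets a masking rule for the PhGA and, in the neighbouring section, an instruction that defeats it unless the physician rates before the review and before the examination. The masking is therefore not secured by the protocol, which is a narrower statement than saying that the PhGA is not independent. The item wording is a separate and plain mismatch with the endpoint.

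Up to 8 PhGA occasions per patient are exposed, wherever one investigator does both tasks. The size of any effect on the scores is unknown. What is weakened is the use of the PhGA as separate corroboration of the patient-reported outcomes. The conflict does not by itself bias the comparison of secukinumab with placebo, and the primary WORC analysis and the sample size are unaffected.

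This rests on two assumptions: that the site operations manual does not already resolve the order, and that the redacted exploratory section contains no other clinician rating. The correction is worth making because it costs little and protects a rule that the sponsor chose.

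**What to change.** In sections 8.6.1 and 8.6.2, and in the site operations manual:

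- Keep the adverse event review before the examination, but exempt the single-line patient global VAS from what the rating investigator sees until the PhGA is recorded and signed.
- Have site staff who are not rating check that page for completeness, as the coordinator already does for the questionnaires. They should pass on any written comment without showing the mark.
- Reword the PhGA item to ask for disease activity over the last 24 hours, so that question, anchors and endpoint agree.

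Moving the whole adverse event review to after the examination would also remove the conflict, but it reverses a stated safety sequence and is not needed.

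The cost is a few sentences, one item wording, and one page handled separately at each visit. The rater will still have seen the WORC and the diary, so the change secures masking to the patient global only. The study report should not describe the PhGA as independent of patient reports.

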8.6.3.1 MRI of the shoulder, Sein score and Bauer score

The MRI Sein score will be used primarily to grade supraspinatus tendinosis at screening using a modified 4-point scale ([Sein et al 2007](#)), and monitor changes in this grading over time as a treatment outcome (secondary objective). Tendinopathy will be characterized by thickened inhomogeneous rotator cuff tendon with increased signal intensity on all pulse MRI sequences, yet not as bright as the fluid on typical T2-weighted images. Since tendonitis and partial thickness cuff injuries are prevalent in sporting activity and in middle age, another grading system, the Bauer score, will be used as an exploratory endpoint for a differentiated assessment of supraspinatus partial tears and tendonitis ([Bauer et al 2014](#)). A 9-point tendinopathy grade will be generated out of this approach, including sub-scores for tendonitis (0-2), tear thickness (0-4) and AP tear size (0-3). Finally these images will also be used to measure thickness of the rotator cuff tendon and assess for presence of bursitis in the area of the rotator cuff.

Enhancement of the subacromial bursa will be assessed. Images will be scored on a scale of 0–2 depending on the maximum thickness of enhancing tissue: 0: no abnormal enhancement; 1: up to 3 mm thickness of enhancing tissue; 2: 3 mm or more enhancing tissue ([Hodgson et al 2012](#)).

Commercially Confidential Information

MR images will be acquired at 3T in multiple planes by using an imaging sequences optimized for tendon/surrounding tissue separation and adapted to the MRI system capabilities. All MRI scans will be sent for central reading and all results obtained post Baseline visit will remain blinded to the investigator, patient and sponsor until after the primary endpoint analysis at week 14. Detailed information can be located in the imaging manual. The coded MRI medical images will be used primarily for analysis as described in this protocol; however, the images may also be used for the development and evaluation of new analysis methods directly related to the area of research that this study covers.

Commercially Confidential Information

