During the 2-week run-in period patients should take NSAIDs/acetaminophen at a stable and adequate (or maximally tolerable) dose, and still have inadequate control of symptoms at randomization. Alternatively NSAID should have been stopped due to intolerance. Patients who tolerate it will continue taking the NSAID regimen from the run-in period. Patients should not increase the NSAID/acetaminophen dose, but can choose to decrease the dose at any time. Dose adjustments are allowed after the primary endpoint at 14 weeks. During first 14 weeks of the study local steroid injection is not allowed. After assessment of the primary endpoint at week 14 patients may have 1 steroid injection during the last 10 weeks observation period. The stable NSAID dosing and avoidance of steroid injections are required in order not to have other variables than AIN457 influencing the effect on the tendinopathy.

The rationale for key design elements in this study include:

Randomization: This decreases the chance of an imbalance in subject characteristics between groups, thereby facilitating a valid basis for the treatment comparison.

Double-blind: Blinding of subjects, investigators and sponsor up to the point of week 14, the primary endpoint, allows for an unbiased assessment of subjective readouts such as the efficacy parameters, especially the PROs and as well for adverse events evaluation. The blinding is maintained for patient and investigator beyond the primary endpoint until the end of the study to ensure reliable efficacy and safety measures. The sponsor will be unblinded after the primary endpoint analysis.

Placebo-controlled: A placebo arm is included in this study because it is not known whether secukinumab can improve tendinopathy, and because there is no disease modifying therapy available. However, standard of care with NSAIDs and physiotherapy will be given to both treatment groups throughout the study, and if required a steroid injected into the tendon can be given also in both groups. Due to the nature of the disease and the outcome measures used, a placebo arm is necessary to obtain reliable efficacy measurements, to judge the size of the active treatment compared to change over time in the placebo group, and to reasonably attribute adverse events to secukinumab.

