6.2 Treatment arms

Patients will be assigned to one of the following 2 treatment arms in a 1:1 ratio, with approximately 50 patients per arm.

- Group 1: Secukinumab 300 mg s.c. (2 x 150 mg)
- Group 2: Placebo s.c. (2 injections)

Treatment is administered at Day 1 (randomization visit), and Weeks 1, 2, 3, 4, 8 and 12.

Subjects who complete the assessments associated with Week 14 visit should continue the study in a (treatment free) follow up period of 10 weeks up to 24 weeks.

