6.4 Treatment blinding

This is a subject, investigator and sponsor-blinded study. Subjects, investigators and sponsor will remain blinded to study treatment throughout the study, except where indicated below.

The identity of the treatments will be concealed by the use of study drugs that are all identical in packaging, labeling, schedule of administration, appearance, and odor.

Site staff

All site staff (including study investigator and study nurse), except the unblinded pharmacist, will be blinded to study treatment throughout the study.

Unblinding a single subject at site for safety reasons (necessary for subject management) will occur via an emergency system in place at the site (see [Section 6.6](#)).

Sponsor staff

All other sponsor staff (study statistician, study programmer, biomarker expert, clinical trial team, decision boards etc.) will stay blinded to treatment assignments (except in the case of a safety event necessitating unblinding) until after database lock for the analysis of the primary endpoint at Week 14. Study monitors will remain blinded throughout the study.

All unblinded personnel will otherwise keep randomization lists and data or information that could unblind other study team members confidential and secure until database lock for the primary endpoint at Week 14.

Following final database lock all roles may be considered unblinded. See [Table 6-2](#) for an overview of the blinding/unblinding plan.

The sample analysts will receive a copy of the randomization schedule (via request to the Randomization Office), to facilitate analysis of the samples. The sample analysts will provide the sample data to the study team under blinded conditions unless otherwise allowed.

The study statistician will be able to access the randomization list for interim analyses and is allowed to share unblinded information with the rest of the clinical team as appropriate for internal decision purposes, as outlined in [Table 6-2](#). For example, unblinded summaries and unblinded individual data can be shared with the team for after the primary endpoint analysis at Week 14.

Study programmers and other personnel involved in study data analysis (e.g. biomarker expert) are allowed to access treatment assignment information for the purpose of conducting the primary endpoint analysis.

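### MRI masking for patient and investigator is required only until the Week 14 analysis, so the protocol permits disclosure before some late-recruited patients give their Week 18 and 24 ratings

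*Protocol*

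**What the plan says.** **MRI results.** Protocol Section 8.6.3.1 sends all scans for central reading and states that "all results obtained post Baseline visit will remain blinded to the investigator, patient and sponsor until after the primary endpoint analysis at week 14". It refers to the imaging manual for detail.

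**Treatment code.** Section 3.2 says: "The blinding is maintained for patient and investigator beyond the primary endpoint until the end of the study to ensure reliable efficacy and safety measures". Under Section 6.4, site staff other than the unblinded pharmacist "will be blinded to study treatment throughout the study", and most sponsor staff stay blinded "until after database lock for the analysis of the primary endpoint at Week 14". Section 6.4 mentions a separate final database lock, and Table 6-2 still shows patients and site staff as blinded at the Week 14 analysis.

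**What follows Week 14.** Section 6.2 says that patients who complete that visit "should continue the study in a (treatment free) follow up period of 10 weeks up to 24 weeks". Section 11.5 lists "Change from baseline in WORC score at weeks 2, 4, 8, 12, 18 and 24" as a secondary variable, and gives QuickDASH, ASES, EQ5D, pain VAS, and the patient and physician global assessments at Weeks 18 and 24 too. It also lists "MRI Sein score at weeks 8, 14 and 24". The Week 8 and Week 14 scans therefore precede the Week 18 and 24 ratings.

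**Other masking rules.** Section 8.6.2 masks the physician to the patient's own global rating and does not mention MRI. The SAP text has no rule on masking MRI results.

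**The concern.** The sponsor can reasonably see the MRI readings after the Week 14 lock. The patient and the investigator are in a different position, because they go on producing data. For anyone still in follow-up at that lock, nothing in the protocol or SAP requires the Week 8 and 14 readings to be withheld before the remaining ratings.

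All the clinical ratings after Week 14 are subjective. A patient or physician who knows that the tendon looks better or worse may score differently. The knowledge could also affect the NSAID changes and the single steroid injection that Section 3.2 allows after Week 14. It could affect whether a patient stays to the end, which matters because SAP Section 4 limits the Day 169 efficacy analysis to patients who completed follow-up.

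MRI is itself a treatment outcome. If the drug changes it, what is disclosed differs by arm and the influence need not cancel. Early- and late-recruited patients would also give the same ratings under different conditions.

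**Working it through.** The plan states no figure on this point, so there is none to reproduce. The check has two parts.

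**1. Does any other text extend the MRI masking?** Sections 3.1, 3.2 and 6.4 and Table 6-2 cover treatment assignment. Section 8.6.2 covers the patient's global rating only. The SAP is silent. So Section 8.6.3.1 stands alone, and its requirement ends at the Week 14 analysis.

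**2. How many patients could be exposed?** Visit days from Table 8-1:
- Week 14: Day 99 ±2
- Week 18: Day 127 ±7
- Week 24: Day 169 ±7

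Time from the Week 14 visit:
- to Week 18: 127 - 99 = 28 days, or 4 weeks (19 to 37 days within the windows)
- to Week 24: 169 - 99 = 70 days, or 10 weeks (61 to 79 days within the windows)

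Two inputs are assumptions, because the documents give neither: recruitment is uniform over R weeks, and readings are released L weeks after the last patient's Week 14 visit. A patient randomized t weeks before the last one is t + L weeks past his or her own Week 14 visit at release. The Week 24 rating is still to come if t + L < 10, and the Week 18 rating if t + L < 4. With t uniform on 0 to R:

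- share exposed at Week 24 = (10 - L)/R, or zero if L ≥ 10
- share exposed at Week 18 = (4 - L)/R, or zero if L ≥ 4

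For example, R = 52 and L = 6 give (10 - 6)/52 = 7.7% at Week 24 and zero at Week 18.

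| R (weeks) | L (weeks) | Week 18 | Week 24 |
|---|---|---|---|
| 26 | 0 | 15% | 38% |
| 26 | 4 | 0 | 23% |
| 26 | 6 | 0 | 15% |
| 52 | 0 | 8% | 19% |
| 52 | 4 | 0 | 12% |
| 52 | 6 | 0 | 8% |
| 104 | 0 | 4% | 10% |
| 104 | 6 | 0 | 4% |
| any | 10 or more | 0 | 0 |

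With about 100 patients randomized, the percentages are also approximate patient counts. The L = 0 rows are upper bounds: release follows the analysis, which follows a database lock, so L must exceed zero.

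**The case against.** The strongest reply is that the sentence sets a minimum masking period and not a release plan. Nothing in the documents describes sending post-baseline readings back to sites, and the imaging manual, which is not available here, may be stricter. That stands: the point concerns what the protocol permits.

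Second, Section 3.2 and Table 6-2 concern the treatment code. A reader might infer that Section 8.6.3.1 unblinds patients or contradicts Section 3.2. It does neither, because knowing one's own MRI grade is not knowing the assignment. What remains is that the stated purpose of reliable measures to study end is not carried through to MRI results.

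Third, the timing is uncertain. The opening of protocol Section 11 says that analysis takes place when the trial ends. If that governed, no one would be exposed. It conflicts with the separate Week 14 lock in Section 6.4, so it cannot be relied on as protection. Even under the Week 14 lock, a lag of 10 weeks or more removes the exposure.

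Fourth, the Week 24 MRI might be thought open to the same bias. It is read centrally, so a patient's or investigator's knowledge could reach it only indirectly, through changed background treatment.

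Fifth, the follow-up comparisons already include treatment changes that become permissible after Week 14. That limits the consequence. It is no reason to leave open a further influence that is easy to close.

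**Conclusion.** The concern holds as a gap in the masking rule for secondary follow-up outcomes. Once the Week 14 analysis is done, the protocol no longer requires MRI results to be masked from patient and investigator, and late-recruited patients may then still have subjective ratings to give.

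On the stated assumptions, the exposed share at Week 24 is at most 19% for R = 52 and 38% for R = 26, falling to 8% and 15% at L = 6 and to none from L = 10. At Week 18 it is at most 8% and 15%, and none from L = 4. Week 24 is therefore the more realistic concern, and the Week 24 shares should not be applied to Week 18.

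The size and direction of any bias cannot be derived from the documents, and a difference between arms would require the drug to change the MRI. Ratings at Week 14 precede any release, so the primary comparison is unaffected. A reader might take the sentence patient by patient, so that everyone is exposed after his or her own Week 14 visit. The documents do not support that: the sentence names the analysis of the primary endpoint, which Section 6.4 ties to a database lock for the trial.

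**What to change.** Split the sentence in protocol Section 8.6.3.1, and match it in the imaging manual:

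- **Investigator and patient:** post-baseline MRI readings stay masked until that patient's end-of-study assessments are complete, or until the final database lock.
- **Sponsor:** readings stay masked until the Week 14 lock, as now intended.
- **Exception:** findings that must be disclosed for safety.

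Also reconcile the opening of Section 11 with Section 6.4, so that the timing of the Week 14 analysis is stated once.

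The change adds no visit, procedure or patient. Its downside is that some patients receive their readings some weeks later.
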